2.3 Exploratory objectives

To characterize predictive immunologic biomarkers of response in tissue and peripheral blood of patients receiving ramucirumab and pembrolizumab combination therapy

Exploratory Endpoints: 1) Baseline tumor immunoprofile by IHC, including tumor infiltrating lymphocytes and T cell receptor (TCR) immunosequencing (immunoSEQ) and relationship to clinical outcomes, including response rate. 2) Circulating immune cell profiles in response to treatment and in relation to clinical response using CyTOF profile on peripheral blood samples. 3) Circulating VEGF at baseline, after treatment and at progression to evaluate correlation with clinical response

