3.2 Study Duration

Patients will receive pembrolizumab and ramucirumab day 1 during each 21-day cycle. Patient may continue on study drugs until disease progression or for up to 35 cycles. Objective assessment of disease progression will be performed every six weeks.

IRB Protocol Number: 2019C0145
IRB Approval date: 06/10/2022
Version: 05/06/2022

PROTOCOL NUMBER: OSU-19132

[figure not shown]
The study enrolled first patient in Summer 2020 with respect to first patient in (FPI). With an expected accrual rate of 1 patients every 2months, and a total number of 34 patients planned (if trial proceeds to second stage), the anticipated enrollment period is 60 months with the last patient enrolled by Summer2025. The anticipated length of treatment period will be approximately 3-6 months, leading to the last patient off study treatment in November-December 2025. The primary endpoint analysis will be done after the last accrued patient has been followed for at least 6 weeks.

IRB Protocol Number: 2019C0145
IRB Approval date: 06/10/2022
Version: 05/06/2022

PROTOCOL NUMBER: OSU-19132

[figure not shown]

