Blood (2 tubes x 10 ML): BD Vacutainer (heparin tubes) will be used for blood collection. Peripheral blood will be analyzed for circulating immune cell profiles in relation to clinical response using CyTOF profile at baseline and prior to cycle 3. Peripheral blood analysis will also include TCR immunosequencing (immunoSEQ) and VEGF (ELISA) at baseline, during treatment and at progression.

Peripheral blood for CyTOF profile will be collected at 3 time points (baseline and cycle 2, day 1 at progression/end of treatment) for the initial 13 patients (stage 1). If a patient discontinues treatment after cycle 2, EOT samples will be collected at that time. Peripheral blood mononuclear cells (PBMC) and plasma for remaining correlative studies (TCR immunoSEQ and VEGF) will be preserved from collected blood samples at 3 time points: baseline (pre-treatment day 1), prior to cycle 3, and at study discontinuation or disease progression. Correlative studies will be collected as scheduled even if one of the two drugs is held/discontinued.

Samples will be stored for batching of correlative studies (TCR immunoSEQ and VEGF).

IRB Protocol Number: 2019C0145
IRB Approval date: 06/10/2022
Version: 05/06/2022

PROTOCOL NUMBER: OSU-19132

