6.4 End of Study

The primary statistical analysis will be performed when 80% of the events for the secondary analysis of PFS have occurred. This will ensure appropriate follow-up time for the primary endpoint of ORR and for the secondary endpoints of PFS and OS.

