9.1.3 Exploratory Endpoints (Correlative Studies)

To characterize predictive immunologic biomarkers of response in tissue and peripheral blood

- T cell receptor (TCR) immunosequencing in peripheral blood (before and after treatment) and tumor tissue (at baseline) with clinical response.
- CyTOF from peripheral blood and infiltrating immune cells in tissue at baseline and after treatment
- Circulating VEGF in peripheral blood at baseline and after treatment with clinical response

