To study the association of immune cell subpopulations among blood and the tumor microenvironment, we will use linear mixed-effects models for repeated measurements within patients. A bivariate plot will be used to describe the relationship between response rate and peak VEGF via ELISA over time. Results will be summarized using descriptive statistics (i.e. means, medians, standard deviations, 95% confidence intervals for continuous variables, and frequencies for discrete data). The limited sample will not provide sufficient power for formal hypothesis testing (except to detect very large differences in these markers), but the preliminary data will be used to explore potential relationships and differences using graphical analyses and quantitative summaries of these markers. These results and exploratory analyses will also be used in planning a future randomized study of this combination treatment regimen in this patient population.

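### The VEGF plot uses a peak with no sampling window, so it can draw on values taken after response is determined and on a number of samples that depends on outcome

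*Combined protocol and SAP*

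**What the plan says.** Section 9.5 gives the whole VEGF analysis in one sentence: "A bivariate plot will be used to describe the relationship between response rate and peak VEGF via ELISA over time". It sets no window for the peak and does not list the samples that count.

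The sections that describe the samples differ:

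- Section 2.3 defines the endpoint as "Circulating VEGF at baseline, after treatment and at progression to evaluate correlation with clinical response".
- Section 9.1.3, the endpoint list in the statistical chapter, has "Circulating VEGF in peripheral blood at baseline and after treatment with clinical response" and does not name progression.
- Section 6.1.3 plans the assay as "VEGF (ELISA) at baseline, during treatment and at progression", with plasma kept "at 3 time points: baseline (pre-treatment day 1), prior to cycle 3, and at study discontinuation or disease progression".

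The objective over these endpoints in section 2.3 is to find immunologic markers that predict response. Section 9.5 calls the correlative work exploratory, says the sample is too small for formal testing, and says the results will help plan a later randomized study.

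**The concern.** A maximum over time has two weaknesses as a marker of response.

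The first is timing. The third sample is drawn when the patient progresses or stops. If the peak falls there, the value on the marker axis was measured after, or together with, the outcome on the other axis. Such a value cannot predict response.

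The second is counting. A maximum tends to grow with the number of values behind it. If responders and non-responders have different numbers of samples when the data are cut, their peaks differ even where VEGF has nothing to do with response.

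At stake is whether a spurious VEGF signal, or a masked one, is carried into the design of the next trial.

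**Working it through.** The plan gives no figure for the VEGF analysis, so there is none to reproduce.

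**Inputs from the documents.** Three sampling times (sections 2.3 and 6.1.3). N = 34 and a target response rate of 25% (section 9.4.1): 0.25 × 34 = 8.5, taken as 9 responders and 25 non-responders. Treatment for up to 35 cycles of 21 days (section 3.1). Two statements on the time of the main analysis: "The primary statistical analysis will be performed when 80% of the events for the secondary analysis of PFS have occurred" (section 6.4) and "The primary endpoint analysis will be done after the last accrued patient has been followed for at least 6 weeks" (section 3.2).

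**Assumptions, because the documents give none.** Log-VEGF is normal with SD 1, with equal correlation ρ between samples from one patient and no true relation to response. The shares of missing samples and any rise at the last sample are varied.

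**1. Timing.** The first scan is at 42 ± 7 days (section 6.3.5). Cycle 3 day 1 is nominally 2 × 21 = 42 days after the first dose. Only the baseline sample clearly precedes the first response assessment. Cycle 3 day 1 roughly coincides with it, and the last sample accompanies or follows progression or stopping.

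**2. Count artefact, ceiling.** For independent standard normal values, E(max of 3) = 3/(2√π) = 0.846 and E(max of 2) = 1/√π = 0.564. The gap is 0.282. With correlation ρ it becomes 0.282 × √(1 − ρ):

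| ρ | gap (SD) |
|---|---|
| 0 | 0.28 |
| 0.5 | 0.20 |
| 0.8 | 0.13 |

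This is the case where every non-responder has three samples and every responder lacks the last.

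**3. Less extreme cases.** If a share f_R of responders and f_N of non-responders each lack one sample, the expected gap (non-responders minus responders) is (f_R − f_N) × 0.282 × √(1 − ρ). Simulation of 34 patients, 3,000 runs per case, ρ = 0.3 to 0.7, gave the results below. AUC is the chance that a random non-responder's peak exceeds a random responder's, and 0.50 means no artefact.

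| Samples available | gap (SD) | AUC |
|---|---|---|
| No responder has the last sample | 0.16 to 0.24 | 0.55 to 0.58 |
| Half the responders lack it | 0.08 to 0.12 | 0.525 to 0.54 |
| No responder has it, and VEGF rises 0.5 to 1 SD at that sample | 0.40 to 0.76 | 0.62 to 0.73 |
| All have it, but one third of non-responders miss cycle 3 day 1 | −0.05 to −0.08 | 0.475 to 0.485 |
| All have three samples, with or without a 1 SD rise | about 0 | 0.50 |

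**4. How many responders could lack the last sample.** With the section 6.4 timing, and assuming all 34 eventually have a PFS event, 0.80 × 34 = 27.2, so about 7 have none. If all 7 were responders still on treatment, f_R = 7/9 = 0.78, and the gap is 0.78 × 0.28 = 0.22 SD at ρ = 0 or 0.78 × 0.13 = 0.10 SD at ρ = 0.8. With the section 3.2 timing, 35 × 21 = 735 days of treatment less 42 days leaves 693 days, about 23 months. At one patient every 2 months, about 12 of the 34 enrolled late enough to be still on treatment. If responders are spread evenly over accrual, f_R is at most about 12/34 = 0.35 on average, and the gap is at most about 0.10 SD at ρ = 0.

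**5. Against noise.** Under the same model the variance of the peak is ρ + (1 − ρ) × 0.559 for three samples and ρ + (1 − ρ) × 0.682 for two. With 25 and 9 patients, the standard error of the group difference is √(0.559/25 + 0.682/9) = 0.31 SD at ρ = 0, and about 0.38 SD at ρ = 0.8.

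**The case against.** The strongest reply is that the plan never says the progression sample enters the peak. Section 9.5 is silent and section 9.1.3 leaves progression out. This stands as a limit on what can be claimed. Still, section 2.3 ties the progression sample to correlation with response, and a peak over time without a window is most naturally read as taking in every sample.

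The second reply is that the last sample is planned for every patient, responders included. Section 3.2 expects about 3 to 6 months of treatment against 60 months of accrual, the samples are stored for batching (section 6.1.3), and no section dates the correlative analysis. If it is run after everyone has stopped, the count artefact is gone. This also stands, but the documents do not commit to waiting.

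The third reply is that the count artefact alone is below one standard error on a single scatter plot that carries no test. That is right. It no longer holds if VEGF also rises at the last sample: 0.40 to 0.76 SD exceeds one standard error.

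A reader might go further and infer that the plan builds in a link between high VEGF and non-response because progressors always contribute three values and responders two. The documents do not support this. Responders also get the last sample. Patients who stop around the end of cycle 2, mostly non-responders, may lack a separate cycle 3 sample and so have two values. The direction is not fixed.

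**Conclusion.** The peak window is undefined. On the natural reading, the peak can come from a sample taken after response is determined, and the number and timing of samples depend on outcome. The plot can be biased in either direction.

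The range of 0.13 to 0.28 SD is a ceiling for the count artefact. It holds only if all responders lack the last sample and no non-responder lacks one. The stated analysis times make smaller values more likely. A rise of VEGF at progression would raise the ceiling, missing cycle 3 samples in early discontinuers can turn the bias slightly negative, and complete sampling removes the count artefact. Complete sampling does not cure the timing problem, which rests on the sampling schedule and not on any assumed figure. The size estimates rest on assumed normality, correlation, missing shares and rise.

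The point is minor. It concerns one exploratory plot and leaves the primary endpoint, sample size and error rates untouched. It is worth correcting because the results are meant to inform a later randomized trial.

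**What to change.** In section 9.5, replace peak VEGF with three separate displays:

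1. Main: baseline VEGF against each patient's best response. This precedes the outcome and should exist for nearly every treated patient. It also replaces response rate, a group quantity, with something that can be plotted per patient.
2. Secondary: change from baseline to cycle 3 day 1, in patients with both samples. Label it an on-treatment description, and note that it roughly coincides with the first scan and omits early discontinuers. Give the number of patients left out, by response.
3. Separate: VEGF at progression or end of treatment, split by reason for stopping and not used as a predictor.

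Align the VEGF time points in sections 2.3, 9.1.3 and 9.5. Only stating a window for the peak would remove the ambiguity, but a maximum of baseline and cycle 3 day 1 would still depend on who reached cycle 3.

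The cost is a few sentences of wording. Samples and assays stay as planned. The one loss is that patients without a cycle 3 sample drop out of the change measure.

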10. DATA MANAGEMENT

10.1 Clinical Data

A Research Study Manager will be assigned to the study. The responsibilities of the RSA include project compliance, data collection, abstraction and entry, data reporting, regulatory monitoring, problem resolution and prioritization, and coordinate the activities of the protocol study team and coordination with the study statistician. The data collected for this study will be entered into a secure database (Clinical Research Database (CRDB)). Source documentation will be available to support the computerized patient record. The principal investigator will maintain ultimate responsibility for the clinical trial.

10.2 Quality Assurance

Weekly registration reports will be generated to monitor patient accruals and completeness of registration data. Routine data quality reports will be generated to assess missing data and inconsistencies. Accrual rates and extent and accuracy of evaluations and follow-up will be monitored periodically throughout the study period and potential problems will be brought to the attention of the study team for discussion and action. Random-sample data quality and protocol compliance audits will be conducted by the study team, at a minimum of two times per year, more frequently if indicated.

11. PROTECTION OF HUMAN SUBJECTS

Prior to the enrollment of each patient, the risks, benefits and objectives of the study will be reviewed with the participant, including a discussion of the possible toxicities and side effects. Alternative, non-protocol, treatment options will be discussed with the patient. It will be reviewed that participation in this clinical trial is voluntary and that the patient may withdraw consent at any time. The study is designed with careful safety monitoring for toxicity including physician visits and serial cardiac monitoring. Specific guidelines for symptom management are in place to protect the study participant.

11.1 Human Subjects Involvement and Characteristics:

All patients who meet the all of the inclusion and none of the exclusion criteria will be eligible. Eligible patients will be 18 years of age or older with a ECOG performance status ≤ 1 and a diagnosis of EGFR mutant NSCLC. Both men and women and members of all ethnic groups are eligible for this trial. Pregnant and breast-feeding women are excluded from this study. This

protocol does not include children because the number of children is expected to be limited for the patient population expected to be accrued onto this study. Also, the majority of children are already accessed by a nationwide pediatric cancer research network. This statement is based on exclusion 4b of the NIH Policy and Guidelines on the Inclusion of Children as Participants in Research Involving Human Subjects.

11.2 Consent process:

All patients at the OSU Thoracic Oncology clinic who meet the inclusion criteria will be eligible. Participation in the trial is voluntary. All patients will be required to sign a statement of informed consent, which must conform to IRB guidelines.

11.3 Possible Toxicities/Side-Effects:

There are risks associated with treatment as described in Section 7; however, patients screened for enrollment will be deemed appropriate for treatment independent of this study.

11.3.1 Benefits

It is unknown if the combination of ramucirumab and pembrolizumab can benefit patients with EGFR mutant lung cancers. The goal of this study is to assess if combination therapy has the potential to demonstrate objective response in patients with lung cancer.

11.3.2 Costs

Patients will be charged for physician visits, routine laboratory tests, and radiologic studies required for monitoring their condition.

The cost of research only biopsies, research related testing/screening, study drugs, as well as correlative analyses will be covered by research funds.

11.3.3 Alternatives

For patients considering this trial as second or third-line therapy or beyond, standard chemotherapy or chemo-immunotherapy may be treatment alternatives.

11.3.4 Confidentiality

Every effort will be made to maintain patient confidentiality. Research and hospital records are confidential. Patients' names and any other identifying information will not be used in reports or publications resulting from this study. Other authorized agencies and appropriate internal personnel (eg. qualified monitors) and external personnel (e.g. qualified monitors from Lilly or Merck), its authorized agents, the FDA, and/or other governmental agencies) may review patient records as required.

11.3.5 Patient safety

Patients are monitored by physicians and oncology nurses who are very familiar with clinical trials. In the case of an adverse reaction, immediate medical attention is available. In the evenings and weekends, we have a 24-hour urgent care facility for outpatients. The PI or co-PI will also be available at all times to organize any necessary intervention.

11.3.6 Monitoring of data to ensure safety

This study is to be monitored by the institutional IRB and Ohio State University Comprehensive Cancer Center Data and Safety Monitoring Committee (DSMC). This incorporates an independent data and safety monitoring board established by arrangement with the National Cancer Institute. The analysis of safety will include all patients. Adverse events, including all toxic effects of treatment, will be tabulated individually, and summarized by severity and causality.

11.3.7 Privacy

The use and disclosure of protected health information pursuant to a completed and signed Research Authorization form may be allowed. The use and disclosure of protected health information will be limited to the individuals described in the Research Authorization form. A Research Authorization form must be completed by the Principal Investigator and approved by the IRB and Privacy Board (IRB/PB).

12. INFORMED CONSENT

Consent must be documented by the participant's dated signature or by the participant's legally acceptable representative's dated signature on a consent form along with the dated signature of the person conducting the consent discussion.

A copy of the signed and dated consent form should be given to the participant before participation in the trial.

The initial informed consent form, any subsequent revised written informed consent form and any written information provided to the participant must receive the IRB/ERC's approval/favorable opinion in advance of use. The participant or his/her legally acceptable representative should be informed in a timely manner if new information becomes available that may be relevant to the participant's willingness to continue participation in the trial. The communication of this information will be provided and documented via a revised consent form or addendum to the original consent form that captures the participant's dated signature or by the participant's legally acceptable representative's dated signature.

Specifics about a trial and the trial population will be added to the consent form template at the protocol level.

The informed consent will adhere to IRB/ERC requirements, applicable laws and regulations and Sponsor requirements.

13. REPORTING REQUIREMENTS

13.1 Adverse Drug Reaction Reporting

Toxicity will be scored using CTCAE Version 5.0 for toxicity and adverse event reporting. A copy of the CTC Version 4.0 can be downloaded from the CTEP homepage (<http://ctep.info.nih.gov>). All appropriate treatment areas have access to a copy of the CTC Version 4.0.

13.2 Serious Adverse Event Reporting (SAE)

An adverse event or suspected adverse reaction is considered “serious” if, in the view of either the investigator, it results in any of the following outcomes:

- Death
- A life-threatening adverse drug experience – any adverse experience that places the patient, in the view of the initial reporter, at immediate risk of death from the adverse experience as it occurred. It does not include an adverse experience that had it occurred in a more severe form, might have caused death.
- Inpatient hospitalization or prolongation of existing hospitalization
- A persistent or significant incapacity or substantial disruption of the ability to conduct normal life functions.
- A congenital anomaly/birth defect.

Important medical events that may not result in death, be life-threatening, or require hospitalization may be considered a serious adverse drug experience when, based upon appropriate medical judgment, they may jeopardize the patient or subject and may require medical or surgical intervention to prevent one of the outcomes listed in this definition.

Examples of such medical events include allergic bronchospasm requiring intensive treatment in an emergency room or at home, blood dyscrasias or convulsions that do not result in inpatient hospitalization, or the development of drug dependency or drug abuse (21 CFR 312.32).

Important medical events as defined above, may also be considered serious adverse events. Any important medical event can and should be reported as an SAE if deemed appropriate by the Principal Investigator.

All events occurring during the conduct of a protocol and meeting the definition of a SAE must be reported to the IRB within 10 days of the investigator’s or research staff member’s learning of the event. Events resulting in temporary or permanent interruption of study activities by the investigator, sponsor, or DSMB to avoid potential harm to subjects should be reported within 48 hours. Events that may represent unanticipated problems involving risks to subjects or others should be promptly reported, regardless of whether they occur during or after the study, or involve a subject who has withdrawn from or completed study participation. If changes to the research or consent process are proposed as a result of the event, or if additional information will be provided to current and/or past participants, an amendment request must also be submitted for IRB review

Serious adverse events will be captured from the time the patient signs consent until 30 days after the last dose of drug. Serious adverse events must be followed until clinical recovery is complete and laboratory tests have returned to baseline, progression of the event has stabilized, or there has been acceptable resolution of the event.

The following detailed information must be recorded for each serious adverse event in the SAE report form:

- A description of the AE in medical terms
- The severity grade as assessed by the investigator according to the definitions in NCI-CTCAE Version 5.0

- The date of becoming serious and the date of becoming known (if different)
- The reason for seriousness
- The outcome of the SAE at the time of the report
- Information on administration of the study drug and chemotherapy and any action taken
- Information on any treatment procedures necessary for the SAE, concomitant medications, relevant lab tests and relevant medical history

If in any one subject the same SAE occurs on several occasions, then the SAE in question must be documented and assessed anew each time.

The investigator is required to submit SAE Follow-up reports until the SAE has resolved or stabilized and all queries have been answered.

13.3 Reporting to FDA:

Serious adverse events will be forwarded to FDA by the Investigator according to 21 CFR 312.32.

It is the responsibility of the PI and the research team to ensure serious adverse events are reported according to the Code of Federal Regulations, Good Clinical Practices, the protocol guidelines, the Investigator's guidelines, and Institutional Review Board policy.

